5.7 Packaging

N/A

5.8 Blinding of Study Intervention

This is an open-label trial, so there will be no blinding for participants and study assessors.

5.9 Receiving, Storage, Dispensing and Return

5.9.1 Receipt of Study Intervention Supplies

N/A

5.9.2 Storage

Details of rTMS device storage will be maintained and overseen by the Harquail Centre for Neuromodulation at Sunnybrook Research Institute and Neuromodulation Program at Waypoint Centre for Mental Health. Existing devices are stored at the two sites. Maintenance and calibration will be according to manufacturer guidance from Brainsway and will be performed according to their standards.

5.9.3 Dispensing of Study Intervention

N/A

5.9.4 Return or Destruction of Study Intervention

N/A

6.0 RESEARCH PROCEDURES

6.1 Research Visits

Prescreening during initial contact through phone, email or REDcap: A delegated research staff will conduct prescreening with the participants during their initial contact call to determine their initial eligibility to be screened in the study. This consists of a set of questions regarding inclusion and exclusion criteria. During pre-screening, we will ask participants to indicate their preferred site (Waypoint or Sunnybrook).

Screening visit (SC): A delegated research staff will conduct the informed consent discussion with the patients at the beginning of the screening visit before the assessments to determine their eligibility to participate in the study (Section 6.2. Table). The informed consent process will include a short quiz of five questions to ensure that the participant understands the key information provided. This quiz will be completed after the ICF is explained and before the participant signs it. The screening visit will confirm eligibility through the eligibility checklist that also relies on administration of the TASS and FTND, and the Mini International Neuropsychiatric Interview (MINI) to screen for psychiatric diagnoses according to the DSM-5. We will also collect demographic information, medical history and current medications. The informed consent and assessments may be performed virtually, depending on the scheduling availability of study staff and the participant (refer to Sections 8.5 and 12.2).

- Informed consent (including informed consent quiz)
- Medical history for underlying diseases
- Basic demographics, such as age, sex at birth
- Mini International Neuropsychiatric Interview (MINI)
- TMS Adult Safety Screening Questionnaire (TASS)
- Smoking Contemplation Ladder
- Target Quit Day, for scheduling the week for TMS treatment[61]
- Concomitant medication log, recorded by its generic name, dosage, and dosing frequency
- Fagerstrom Test of Nicotine Dependence (FTND). The FTND is a measure of physical dependence severity.

Baseline visit (BL):

The baseline visit will consist of urine testing using point-of-care dip testing, a concomitant medication survey, and self-report questionnaires. All components of the baseline visit must be completed within 30 days prior to W1D1; otherwise, they should be reassessed.

For the urine drug panel test at the baseline visit (BL) and at the fifth day of Week1 (W1D5), which includes opioids, stimulants, and alcohol, the rationale is that intoxication or withdrawal from stimulants or alcohol may affect the safety of receiving TMS. While the use of non-nicotine substances does not determine eligibility, participants will be advised to refrain from using these substances during treatment in Week 1. However, if the use of a non-nicotine substance demonstrates clinical instability to the extent that continued participation would not be in the best interest of the participant, PI and the study investigator team may decide to discontinue their involvement at PI and Site-PI's discretion (refer to Section 4.7.1). The final eligibility will be determined by the site PIs based on information collected at the screening and baseline visits.

The screening and baseline visits may be completed on site in a single day, depending on research staff availability and participant preference.

Urine testing:

- Urine drug panel, to test recent substance use, including opioids, stimulants, and alcohol, as intoxication or withdrawal from stimulants or alcohol may affect the safety of receiving TMS
- Urine pregnancy test, if required. To confirm pregnancy status, as pregnancy is an exclusion criterion.
- Urine cotinine test (threshold: 200 ng/ml) to confirm recent cotinine use.

Self-report questionnaires:

- Timeline Follow-Back (TLFB) – Amount of cigarette used every day since the last follow-up
- Fagerstrom Test of Nicotine Dependence (FTND). The FTND is a measure of physical dependence severity.
- Tobacco Craving Questionnaire-Short-Form (TCQ-SF), to measure smoking craving.
- Minnesota Nicotine Withdrawal Scale (MNWS), to measure the nicotine withdrawal symptoms.
- Patient Health Questionnaire (PHQ-9), to track the possible effects of TMS on depression symptoms.
- General Anxiety Disorder-7 (GAD-7), to track the possible effects of TMS on anxiety symptoms.
- Altman Self-Rating Mania Scale (ASRM), to track the possible effects of TMS on developing manic/hypomanic symptoms.

Treatment period (Week 1)

Accelerated deep TMS will be administered daily, with four sessions per day, lasting approximately 3 hours (refer to Section 5.4), along with assessments for safety/adverse effects and scales for nicotine dependence, craving, and withdrawal symptoms.

Participants' activities were not systematically controlled during treatment sessions or during the intersession intervals; participants were allowed to do light cognitive activities such as reading or using their computer or smartphone.

On each day of Week 1, the TCQ-SF will be administered twice to measure nicotine craving—once before and once after the aTMS treatment.

Brief counseling for smoking cessation, adapted from the Mayo Clinic's 'Smoke Free and Living It' manual, will be administered at W1D1 and W1D5. The brief counseling sessions may also be offered remotely, based on participant preference and logistical feasibility.

The first day of Week 1 (W1D1)

- Concomitant medication log, recorded by its generic name, dosage, and dosing frequency
- Timeline Follow-Back (TLFB) – Amount of cigarette used every day since the last follow-up
- Tobacco Craving Questionnaire-Short-Form (TCQ-SF), to measure smoking craving. TCQ-SF will be administered twice—once before and once after the aTMS treatment.
- Minnesota Nicotine Withdrawal Scale (MNWS), to measure the nicotine withdrawal symptoms.
- Urine drug panel
- Urine pregnancy test, if required
- Brief counseling for smoking cessation, adapted from the Mayo Clinic's 'Smoke Free and Living It' manual.
- Resting motor threshold measurement
- Accelerated deep TMS treatment
- Adverse event log

The second, third, and fourth days of Week 1 (W1D2, W1D3, W1D4)

- Concomitant medication log, recorded by its generic name, dosage, and dosing frequency
- Timeline Follow-Back (TLFB) – Amount of cigarette used every day since the last follow-up
- Tobacco Craving Questionnaire-Short-Form (TCQ-SF), to measure smoking craving. TCQ-SF will be administered twice—once before and once after the aTMS treatment.
- Minnesota Nicotine Withdrawal Scale (MNWS), to measure the nicotine withdrawal symptoms.

- Accelerated deep TMS treatment
- Adverse event log

The fifth day of Week 1 (W1D5)

At the end of Week 1 (W1D5), a urine cotinine test will be performed, alongside TLFB to determine 7-day point-prevalence abstinence.

At W1D5, for acceptability assessment, a TMS Experience Questionnaire will be administered. Participants will be asked to retrospectively rate (from 1=not at all to 5=very much so) 15 items querying their perceptions of the treatment, its side effects, and its benefits as well as their preferences regarding treatment format and logistics.

- Concomitant medication log, recorded by its generic name, dosage, and dosing frequency
- Timeline Follow-Back (TLFB) – Amount of cigarette used every day since the last follow-up
- Fagerstrom Test of Nicotine Dependence (FTND). The FTND is a measure of physical dependence severity.
- Tobacco Craving Questionnaire-Short-Form (TCQ-SF), to measure smoking craving. TCQ-SF will be administered twice—once before and once after the aTMS treatment.
- Minnesota Nicotine Withdrawal Scale (MNWS), to measure the nicotine withdrawal symptoms.
- Patient Health Questionnaire (PHQ-9), to track the possible effects of TMS on depression symptoms.
- General Anxiety Disorder-7 (GAD-7), to track the possible effects of TMS on anxiety symptoms.
- Altman Self-Rating Mania Scale (ASRM), to track the possible effects of TMS on developing manic/hypomanic symptoms
- Accelerated deep TMS treatment
- Adverse event log
- Urine drug panel
- Urine pregnancy test, if required
- Urine cotinine test (threshold: 200 ng/ml)
- TMS Experience Questionnaire
- Brief counseling for smoking cessation, adapted from the Mayo Clinic's 'Smoke Free and Living It' manual.

Follow-up period (Week 3, 5, 9)

During the Week 3, Week 5, and Week 9 visits, a urine cotinine test and TLFB will be administered to determine 7-day point-prevalence abstinence. Side effect evaluation and brief smoking counseling will also be provided at these three visits, along with

assessments for nicotine dependence, withdrawal, craving, and symptoms of depression, anxiety, and mania.

- Concomitant medication log, recorded by its generic name, dosage, and dosing frequency
- Timeline Follow-Back (TLFB) – Amount of cigarette used every day since the last follow-up
- Fagerstrom Test of Nicotine Dependence (FTND). The FTND is a measure of physical dependence severity.
- Tobacco Craving Questionnaire-Short-Form (TCQ-SF), to measure smoking craving.
- Minnesota Nicotine Withdrawal Scale (MNWS), to measure the nicotine withdrawal symptoms.
- Patient Health Questionnaire (PHQ-9), to track the possible effects of TMS on depression symptoms.
- General Anxiety Disorder-7 (GAD-7), to track the possible effects of TMS on anxiety symptoms.
- Altman Self-Rating Mania Scale (ASRM), to track the possible effects of TMS on developing manic/hypomanic symptoms
- Adverse event log
- Urine cotinine test (threshold: 200 ng/ml)
- Brief counseling for smoking cessation, adapted from the Mayo Clinic's 'Smoke Free and Living It' manual.

Follow-up period (Week 13 and 26)

During the Week 13 and 26 visit, a urine cotinine test and TLFB will be administered to determine prolonged abstinence and continuous abstinence. Three-month or six-month prolonged abstinence is defined as abstinence from the end of treatment (W1D5) to the end of follow-up (Week 13 or 26), while three-month or six-month continuous abstinence is defined as abstinence from the target quit day (in Week 1) to the end of follow-up (Week 13 or 26). Assessments for nicotine dependence, withdrawal, craving, and symptoms of depression, anxiety, and mania will also be performed.

- Concomitant medication log, recorded by its generic name, dosage, and dosing frequency
- Timeline Follow-Back (TLFB) – Amount of cigarette used every day since the last follow-up
- Fagerstrom Test of Nicotine Dependence (FTND). The FTND is a measure of physical dependence severity.
- Tobacco Craving Questionnaire-Short-Form (TCQ-SF), to measure smoking craving.
- Minnesota Nicotine Withdrawal Scale (MNWS), to measure the nicotine withdrawal symptoms.
- Patient Health Questionnaire (PHQ-9), to track the possible effects of TMS on depression symptoms.

- General Anxiety Disorder-7 (GAD-7), to track the possible effects of TMS on anxiety symptoms.
- Altman Self-Rating Mania Scale (ASRM), to track the possible effects of TMS on developing manic/hypomanic symptoms
- Adverse event log
- Urine cotinine test (threshold: 200 ng/ml)
- Brief counseling for smoking cessation, adapted from the Mayo Clinic's 'Smoke Free and Living It' manual.

All assessments and surveys during research visits can be completed in one of two ways, based on participant preferences or each site's standard data collection practices:

1. **Paper option:** Assessments and surveys printed from REDCap will be completed by hand. A study delegate will review the paper source for completeness and accuracy and enter the data into REDCap.
2. **Electronic:** A study delegate will log into REDCap and will remain present while the participant enters their responses to assessments on an electronic device (e.g., computer, iPad). The study delegate will review the assessment for completeness before saving and help the participant navigate to the next assessment or survey, as necessary.

Procedures for addressing active suicidal ideation during research visits can be found in [Section 8.5 \(Safety Management Plan\)](#).

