2.0 CLINICAL TRIAL OBJECTIVES

We will test, for the first time, the overall feasibility of bilateral accelerated deep transcranial magnetic stimulation (deep aTMS) for smoking abstinence, including measures of tolerability, acceptability, retention, and adherence. Our secondary objectives are to assess the effects of deep aTMS on short-term point prevalence abstinence—measured by self-reported abstinence over the past 7 days and confirmed with urine cotinine—at the end of treatment (Week 1), and at Weeks 3, 5, 9, 13, and 26, as well as prolonged and continuous abstinence rates at Weeks 13 and 26. We also aim to explore the potential for rapid onset of effect, along with its impact on attenuating craving, reducing cigarette consumption, and decreasing dependence severity throughout the study.

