3.0 CLINICAL TRIAL DESIGN

3.1 Overall Design

This clinical trial is designed as a one-arm, open-label study to evaluate the efficacy and feasibility of the H4 deep accelerated transcranial magnetic stimulation (aTMS) protocol for smoking cessation. The absence of a control group is intentional, as this pilot study focuses on assessing the intervention's preliminary efficacy in a single arm of 40 participants with tobacco use disorder who are motivated to quit, aiming for 30 completers to guide a future controlled trial. Each participant's involvement will last 26 weeks, starting with a screening phase at Week 0, followed by a one-week treatment period in Week 1, and concluding with follow-up visits at Weeks 3, 5, 9, 13, and 26. The entire trial is expected to span approximately 2 years, covering recruitment, treatment, and follow-up for all participants.

During Week 1, participants will receive 20 rTMS sessions using the Health Canada-approved H4 deep TMS coil, administered at four sessions per day over five consecutive days, targeting the insular cortex, alongside brief counseling adapted from the Mayo Clinic's 'Smoke Free and Living It' manual. Daily assessments will monitor safety, Timeline Followback (TLFB), and nicotine craving and withdrawal symptoms. The primary outcome is overall feasibility, including measures of tolerability, acceptability, retention, and adherence. Secondary outcomes include 7-day point prevalence abstinence—verified by self-report and urine cotinine levels (<200 ng/mL)—at the end of treatment and at Weeks 3, 5, 9, 13, and 26. We will also assess 3-month abstinence at Week 13 and 6-month abstinence at Week 26, both verified by continuous self-reported abstinence during

the respective periods and corresponding urine cotinine levels. Factors such as comorbidities, pre-existing tobacco use disorder severity, or motivation level for abstinence may influence results; these are addressed through eligibility criteria and statistical adjustments.

It is anticipated that a proportion of enrolled participants may not proceed to the treatment phase (Week 1) due to scheduling, logistical, or personal factors. These individuals will be classified as early dropouts and excluded from the intent-to-treat analysis, which will include only participants who initiate at least one TMS session.

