5.0 STUDY INTERVENTION

5.1 Description

Treatment will be delivered through the H4 coil (Brainsway, Israel) and Brainsway stimulator system, generally following previously established reports[41]. Week 1, the treatment period, will begin on the participant's Target Quit Date (TQD), which will be standardized to coincide with the first day of TMS, as smokers are believed to be most susceptible to relapse during the early abstinence phase[61]. However, this may vary due to scheduling constraints. Resting motor threshold (RMT) will be established to determine stimulation intensity at the beginning of the treatment course. This is obtained by finding the optimal position of the helmet that elicits reliable activation of the right abductor pollicis brevis muscle, before then aligning the helmet symmetrically and moving it 6 cm anteriorly. Titration of stimulus intensity may occur to enhance tolerability. Stimulation intensity will be set at 120% RMT, with a minimum of 90% RMT if there are issues with tolerability. Initial sessions may start at a lower intensity (approximately 70% RMT) and increase accordingly. Sixty trains of 30 pulses each (total 1,800 pulses) will be applied at 10 Hz, for 3 second trains, with a 15 second inter-train interval, for approximately 18 minutes of treatment time. For each day within Week 1, four sessions will be administered, with an intersession interval of 30 minutes. TMS could be reschedule the next week in case of holidays, hospital closure or other factors that prevent booking the subjects.

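### With the quit date set at W1D1, the 7-day abstinence reading on W1D5 looks back 2 or 3 days before it, so an on-schedule quitter is scored non-abstinent

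*Protocol*

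**What the plan says.** The 7-day window is attached to end of treatment in several places. Section 2.0 describes point prevalence as "self-reported abstinence over the past 7 days and confirmed with urine cotinine—at the end of treatment (Week 1"), and Section 3.1 repeats it: "Secondary outcomes include 7-day point prevalence abstinence—verified by self-report and urine cotinine levels (<200 ng/mL)—at the end of treatment". Section 3.3 lists end of treatment as the first time point of secondary endpoint 1. Section 6.1 fixes the day of the reading: "At the end of Week 1 (W1D5), a urine cotinine test will be performed, alongside TLFB to determine 7-day point-prevalence abstinence". The schedule in Section 6.2 also lists point prevalence abstinence from the end of treatment onward.

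The treatment calendar is given separately. Section 3.1 has the sessions "administered at four sessions per day over five consecutive days". Section 5.1 starts treatment on the "Target Quit Date (TQD), which will be standardized to coincide with the first day of TMS". It then adds: "However, this may vary due to scheduling constraints". It also says: "TMS could be reschedule the next week in case of holidays, hospital closure or other factors that prevent booking the subjects".

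Section 7.2 enters end of treatment as one of six categorical time levels in a mixed effect logistic regression for abstinence.

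**The concern.** A 7-day look-back read on the fifth day after quitting starts must include days before the quit. Nothing in the protocol shortens the window or gives a grace period for this visit. Nor are participants asked to stop before W1D1: the only abstinence instruction for Week 1, in Section 5.1, is at least 2 hours without smoking before each visit. Section 4.4.2 excludes people who report abstinence in the 3 months before screening, so participants enter as smokers.

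On the standard calendar, the end-of-treatment figure therefore credits people who stopped before treatment and misses those who stopped when it began. This matters because Section 2.0 also aims to "explore the potential for rapid onset of effect", and the first point-prevalence reading that can credit an on-schedule quitter is Week 3. Daily craving scores and TLFB can still inform that aim, so the loss is to one endpoint reading and not to the whole question.

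**Working it through.** The protocol gives no figure to reproduce; the check is a day count.

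**Inputs.** Window length 7 days (Section 2.0). Reading on W1D5, taken as day r = 5 (Section 6.1). Standard quit date on W1D1, day q = 1 (Section 5.1). Five consecutive treatment days (Section 3.1). Day 0 is the day before W1D1. The protocol does not say whether the visit day belongs to the window, so both readings are shown.

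**Formula.** The window begins on day r − 6 if the visit day is counted and on day r − 7 if it is not. The number of window days before the quit date is q minus the first window day, with a minimum of 0 and a maximum of 7.

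- Visit day counted: window is days −1 to 5; 1 − (−1) = 2 pre-quit days; 2/7 = 29%; 5 post-quit days.
- Visit day not counted: window is days −2 to 4; 1 − (−2) = 3 pre-quit days; 3/7 = 43%; 4 post-quit days.

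**If the quit date moves while the reading stays on day 5:**

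| Quit date | Pre-quit days, visit day counted | Pre-quit days, not counted |
|---|---|---|
| Day −2 (3 days before W1D1) | 0 | 0 |
| Day −1 (2 days before W1D1) | 0 | 1 |
| Day 0 (1 day before W1D1) | 1 | 2 |
| Day 1 (W1D1, the standard) | 2 | 3 |
| Day 2 | 3 | 4 |
| Day 3 | 4 | 5 |

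With the reading on day 5, the window is free of pre-quit days only if the quit comes at least 2 (counted) or 3 (not counted) days before W1D1.

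**If the reading moves while the quit date stays on day 1:** r − 6 ≥ 1 gives r ≥ 7 (counted), and r − 7 ≥ 1 gives r ≥ 8 (not counted). The fifth treatment day would have to slip to day 7 or day 8.

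**Later visits.** If the Week 3 visit falls no earlier than day 15, its window begins no earlier than day 9 (counted) or day 8 (not counted), wholly after the quit date. Week 3 onward is unaffected.

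**Conditional worst case.** If every participant smoked up to an on-schedule quit, the end-of-treatment rate would be 0% by construction. For scale, the exact upper 95% limit for zero events is 1 − 0.025^(1/n): 11.6% for n = 30 and 8.8% for n = 40. Those limits would describe the scoring rule and not the treatment. A time level with no events also has no finite maximum-likelihood estimate in the Section 7.2 model.

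**The case against.** The strongest reply is that the calendar is not rigid. Section 5.1 lets the quit date vary and lets TMS move to the following week, and some such departures would make the 7-day window fit. That stands, and it limits the claim about who can be scored abstinent to the standard calendar. It does not repair the standard case. The departures are of unstated number and direction, and a quit date later than W1D1 makes the overlap worse. Where a departure does help, a participant's score depends on scheduling.

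A second reply is that the reach is small: one of six time points of a secondary endpoint, in a one-arm feasibility pilot whose Section 7.1 sets no power target or success threshold for abstinence. That also stands, and it governs how much weight the point deserves. Leaving the matter to a statistical analysis plan is not an answer, because the protocol itself fixes the window, the reading day and the quit date.

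Three stronger readings are tempting, but the document does not support them:

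- A reader might infer a contradiction with continuous abstinence, which Section 6.1 counts from the target quit day. Someone who stops on W1D1 for good would be continuously abstinent at Weeks 13 and 26 but non-abstinent on W1D5. The two measures simply start on different days; this is not a contradiction.
- A reader might infer that the end-of-treatment rate will be 0% and the model will fail. That requires every participant to smoke up to an on-schedule quit. One participant scored abstinent at that visit removes the zero-event level, and the number who depart from schedule cannot be derived.
- A reader might infer that every mention of end-of-treatment abstinence is at fault. Secondary Aim 1 in Section 2.2 attaches point prevalence only to Weeks 3 to 26, and Section 7.2 speaks only of abstinence at end of treatment. The explicit 7-day wording is in Sections 2.0, 3.1, 3.3 and 6.1.

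**Conclusion.** The point holds for the standard calendar: quit date on W1D1, five consecutive treatment days, reading on W1D5. There, 2 of 7 or 3 of 7 window days, depending on whether the visit day is counted, precede both the quit date and any TMS. A participant who smokes up to the quit date and then stops completely is scored non-abstinent, because the self-report part fails whatever the cotinine result. No assumption about cotinine elimination is needed.

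The affected items are the end-of-treatment proportion in secondary endpoint 1 and the matching time level in the mixed logistic model. The primary feasibility endpoint, point prevalence from Week 3 onward, and prolonged and continuous abstinence are not affected. This should be corrected because the stated rule gives a misleading figure at its first time point, but it does not threaten the trial's main conclusions.

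**What to change.** Reconcile Sections 2.0, 3.1, 3.3, 6.1 (W1D5) and 6.2 with the quit-date rule in Section 5.1, and carry the change into Section 7.2. Section 2.2 needs little or no change. Only the measurement wording changes; the treatment calendar and the quit-date rule stay as they are.

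- At end of treatment, replace the 7-day measure with abstinence from the target quit date to W1D5, taken from the daily TLFB.
- Report it as a separate proportion with an exact 95% confidence interval, in two forms: self-report alone, and self-report with W1D5 urine cotinine below 200 ng/mL.
- State the number of days covered for participants whose quit date is not W1D1.
- Make Week 3 the first 7-day point-prevalence time point, including in the mixed model.

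Daily TLFB and the W1D5 cotinine test are already scheduled, so the cost is protocol wording. There are two small downsides. The end-of-treatment figure no longer shares a definition or window length with the later visits, and its self-report form lacks the biochemical confirmation that Sections 2.0 and 3.1 attach to abstinence, which is why both forms should be reported.

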3.2 Primary Endpoints

The overall feasibility of accelerated deep TMS (aTMS) for smoking abstinence: assessed through tolerability (frequency of side effects reported at each visit during Week 1), acceptability (self-reported ratings collected at the end of treatment), retention rate (the proportion of participants who completed the full study), and adherence rate (the proportion of completed sessions among participants who initiated treatment).

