4.7 Participant Withdrawal Criteria

4.7.1 When and How to Withdraw Participants

Patient participants are free to withdraw from participation in the clinical trial at any time. Completion of the study visits involving doing self-report surveys or semi-structured interviews do not have any withdrawal criteria except clinical instability precluding them from safely engaging in the assessment, as determined by the Lead PI/Site-PI.

For the Week1, accelerated deep TMS treatment period: An investigator will discontinue or withdraw a participant for the following reasons:

- Requires in-patient psychiatric hospitalization.
- Develops clinically significant hypomanic or manic symptoms. Possible hypomanic or manic syndromes may be identified by study staff and a study physician will be immediately notified to conduct an assessment.
- Cannot tolerate stimulation at 90% RMT on ≥ 5 treatment sessions overall.
- Develops any medical illness that may be unstable or experience a seizure.
- If a participant must miss rTMS treatments because of COVID-19 symptom screening/exposure restrictions and are not allowed to be on-site, those sessions will not count towards having to discontinue from study treatment per withdrawal criteria. It will be at the discretion of the investigators on a case-by-case basis if a participant needs to discontinue treatment during the trial should the absence secondary to COVID-19 symptom restrictions be prolonged.

For the entire study period: An investigator may discontinue or withdraw a participant for the following reasons:

- Pregnancy
- Withdraws consent.

- Meets an exclusion criterion (either newly developed or not previously recognized) related to safety that precludes further treatment.
- Demonstrates clinical instability to the point where further participation in the study would not be in the best interests of the participant, at the discretion of the PI and the study investigator team.

The reason for participant discontinuation or withdrawal from the study will be recorded within the participant's research record, and/or legal health record. Data up to the point of their last visit may be included in the analysis.

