4.7.2 Follow-up for Withdrawn Participants

If a participant withdraws consent, they can also request the withdrawal of their data subject to any research-specific restrictions, unless the data has already been de-identified and shared. Once withdrawn from the clinical trial, no further research procedures or evaluations will be performed, or additional research-specific data collected on the participant. Reasonable effort will be made to obtain permission to document the reason for withdrawal.

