4.7.3 Early Termination Visit

If a patient participant withdraws from the clinical trial, they will be asked to attend an Early Termination Visit. This includes all assessments included in the post rTMS treatment visit as well as:

- Assessment of new and ongoing AEs.
- Assessment of any complications following the study intervention.
- Documentation of all concomitant medications.

The PI will ensure the participant is appropriately followed for any additional care as required. Data collected until the time of withdrawal may be used in analyses.

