6.2 Schedule of Events

Below is the table outlining the assessments, measures, and treatments done at each visit.

	Screening	Baseline	Treatment					Follow-ups				
Week			W1					W3	W5	W9	W13	W26
Visit Code/Number	SC	BL	W1D 1	W1D 2	W1D 3	W1D 4	W1D 5	W3	W5	W9	W13	W26
Assessments & Measures	In-person visit		X	X	X	X	X	X	X	X	X	X
	ICF	X										
	Contact & Demographic Form	X										
	Medical history	X										
	MINI	X										
	TASS	X										
	Smoking Contemplation Ladder	X										
	Quit day plan	X										
	Concomitant Medication Log	X	X					X	X	X	X	X
	Urine Drug Panel		X	X				X				
	Urine Pregnancy Test (if required)			X	X			X				
	TLFB(Cigarettes)		X	X	X	X	X	X	X	X	X	X
	FTND	X	X					X	X	X	X	X
	TCQ-SF (regular or pre-TMS)		X	X	X	X	X	X	X	X	X	X
	TCQ-SF (post-TMS)			X	X	X	X					
	MNSW		X	X	X	X	X	X	X	X	X	X
	PHQ-9		X					X	X	X	X	X
	GAD-7		X					X	X	X	X	X
	ASRM		X					X	X	X	X	X
	AE Log			X	X	X	X	X	X	X	X	X
	Counseling			X				X	X	X	X	X
	Urine cotinine test		X					X	X	X	X	X
	Confirm eligibility			X								
Treat	TMS Experience Questionnaire							X				
	Point Prevalence Abstinence							X	X	X	X	X
	Prolonged Abstinence										X	X
	Continuous Abstinence										X	X
Treat	RMT for TMS			X								
	TMS			X	X	X	X					

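### Acceptability is scheduled to be rated only at W1D5, and the protocol does not assure a rating from participants who stop TMS before day 5

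*Protocol*

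**What the plan says.** Section 3.2 makes acceptability part of the primary endpoint: "acceptability (self-reported ratings collected at the end of treatment". Section 6.1 names the instrument and its timing: "At W1D5, for acceptability assessment, a TMS Experience Questionnaire will be administered". The content is described there as follows: "Participants will be asked to retrospectively rate (from 1=not at all to 5=very much so) 15 items querying their perceptions of the treatment". The items also cover side effects, benefits, and preferences on format and logistics. The form is not in the visit lists for W1D1 to W1D4, Weeks 3, 5 and 9, or Weeks 13 and 26. The row for "TMS Experience Questionnaire" in the Schedule of Events (6.2) carries a single mark.

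Section 4.7.1 foresees stopping during Week 1. One listed reason to discontinue or withdraw a participant is "Cannot tolerate stimulation at 90% RMT on ≥ 5 treatment sessions overall". For people who leave, 4.7.3 says "If a patient participant withdraws from the clinical trial, they will be asked to attend an Early Termination Visit" and defines its content thus: "This includes all assessments included in the post rTMS treatment visit as well as". Section 4.7.2 says "Once withdrawn from the clinical trial, no further research procedures or evaluations will be performed".

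**The concern.** The questionnaire asks how participants experienced the treatment and its format. People who stop because of discomfort or burden are plausibly those who would rate four sessions a day lowest. If the form reaches only those still present on day 5, the acceptability result describes people who tolerated the course, yet it would be read as describing everyone who started. Section 3.1 says the pilot is meant to guide a future controlled trial, so the stoppers' views bear directly on its purpose. This is a matter of data collection. How missing ratings are analysed may be set in a SAP that is not at hand, but no analysis can recover a rating that was never taken.

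**Working it through.** **1. Who is covered.** Three paths through Week 1 are possible.

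- *Completes five days.* Rated at W1D5.
- *Stops TMS and withdraws from the trial.* Section 4.7.3 requests a visit with the assessments of a post-treatment visit, but no visit in 6.1 or 6.2 has that name. Read as W1D5, it includes the questionnaire. Read as the first visit after the treatment week (Week 3), it does not, because the Week 3 list omits the form. Section 4.7.2 rules out any evaluation after withdrawal, which contradicts both readings.
- *Stops TMS but stays in follow-up.* This path is allowed: 4.7.1 speaks of discontinuing or withdrawing, and the analysis set in 7.2 keeps anyone with at least one session whether or not treatment was completed. Section 4.7.3 does not apply to them. No sentence says whether the form moves to the stopping day or stays at W1D5.

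**2. Whether stopping before W1D5 is possible.** Section 5.2 gives four sessions a day, so the fifth session falls on day 2. The tolerability criterion in 4.7.1, which needs at least five sessions, could therefore be met on day 2 at the earliest.

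**3. The plan's own attrition figure.** The summary gives 40 participants and 30 completers. 40 - 30 = 10; 10/40 = 25%; 30/(1 - 0.25) = 40. This agrees with the 10 subjects (25%) in 7.2. There, however, the figure is a trigger for comparing baseline characteristics and not a forecast of Week 1 stopping. The protocol states no target, standard deviation or precision for acceptability.

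**4. Size of a possible overstatement.** Let d be the share of treated participants who stop before W1D5, C and S the mean ratings of completers and stoppers, and g = C - S.

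- Mean over all treated: (1 - d)C + dS.
- Mean if no stopper is rated: C. Overstatement: d × g.
- If a share c of stoppers is rated, the overstatement is (1 - d)g / [(1 - d) + dc] - (1 - d)g.

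The gap g is an assumption, taken as 1 to 2 points; the protocol gives no value. For d, 2% is the dropout attributed to side effects in the accelerated-TMS review cited in 1.5, 10% is an assumed middle value, and 25% is the figure from step 3, used as an upper bound.

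| d | No stopper rated (c = 0) | Half rated (c = 0.5) | All rated (c = 1) |
|---|---|---|---|
| 2% | 0.02-0.04 | 0.01-0.02 | 0 |
| 10% | 0.10-0.20 | 0.05-0.10 | 0 |
| 25% | 0.25-0.50 | 0.11-0.21 | 0 |

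Example with d = 0.10 and g = 2: with none rated, 0.10 × 2 = 0.20; with half rated, 1.8/0.95 - 1.8 = 0.095. If g = 0, the overstatement is zero at any d.

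**The case against.** A reader might infer that early stoppers give no rating and that acceptability is biased upward as a matter of design. The protocol does not support this.

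- The Early Termination Visit is a route to a rating, and the more natural reading of its content is W1D5. Section 6.1 labels the Week 3, 5 and 9 visits as follow-up and treats W1D5 as the end of treatment.
- No sentence cancels W1D5 for someone who stops stimulation but stays. The visit also carries the end-of-treatment cotinine, TLFB and symptom scales, and 7.2 analyses end-of-treatment abstinence in everyone with at least one session.
- Section 8.5 already allows self-report questionnaires to be done virtually.
- Early stopping would show in adherence, retention and the Week 1 side-effect reports. Acceptability has no threshold that a few tenths of a point could tip.

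These points stand, and they reduce the concern from an established bias to a risk. They do not remove it. The favourable reading has to be inferred, 4.7.2 contradicts it for those who withdraw, and two sites could apply it differently. The other components record that a person stopped; they do not record how that person judged the format.

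The 25% row should not be read as the expected case. The loss from 40 to 30 also covers follow-up to Week 26 and may include enrolled people who never start TMS, whom 3.1 excludes from the intent-to-treat analysis. The 2% figure covers only dropout due to side effects, so total Week 1 stopping could be higher, but the protocol gives no such figure.

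**Conclusion.** The concern holds as a gap in collection: a rating from participants who stop TMS before day 5 is not assured, so acceptability may be overstated. The direction rests on the assumption that early stoppers would rate the format lower than completers. The size rests on the assumed 1 to 2 point gap and on the unknown share left unrated. It is a few hundredths of a point if that share is near 2%, 0.10-0.20 at 10%, at most 0.25-0.50 at 25%, and nil if every stopper is rated. An upward bias is not established by the documents. The point is worth acting on because the repair is cheap and has to be in place before participants are treated.

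**What to change.** - In 6.1 and 6.2, give the TMS Experience Questionnaire at W1D5 or, for anyone with at least one TMS session who stops earlier, at the point of stopping (remotely if needed), whether or not the person leaves the trial. Align the timing words in 3.2.
- In 4.7.3, replace the undefined visit label with the W1D5 assessments and name the questionnaire, to be given if not already completed.
- Reconcile 4.7.2 with 4.7.3, so that the Early Termination Visit is offered with the participant's agreement.
- Report the number rated out of the number treated. This line may sit in the SAP.

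The cost is a few lines of text and one schedule footnote; the 15-item form already exists. There are two drawbacks: mean acceptability may look slightly less favourable, and ratings taken at early stopping reflect a shorter exposure, so they are best shown separately as well as pooled.
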